2. STUDY OBJECTIVES

2.1. Primary objective

Primary Objective:	Outcome Measure:
To evaluate the safety and tolerability of ceftaroline for the treatment of LOS in neonates and young infants aged 7 to <60 days	Safety evaluations will be conducted in the Safety Analysis Set and assessments will include AEs, SAEs, deaths, and discontinuations due to AEs.

2.2. Secondary objectives

Secondary Objective:	Outcome Measure :
To evaluate the PK profile of ceftaroline in neonates and young infants aged 7 to <60 days with LOS	Concentrations of ceftaroline fosamil, ceftaroline, and ceftaroline M-1 in plasma (and if available, concentrations of ceftaroline and ceftaroline M-1 in cerebrospinal fluid [CSF])
Evaluate the efficacy of ceftaroline for the treatment of LOS in neonates and young infants aged 7 to <60 days	Efficacy outcome measures will include clinical outcome at EOT and TOC in the Modified Intent-to-Treat (MITT) Analysis Set.

2.3. Safety objectives

Safety is the primary objective.

2.4. Exploratory objectives (not applicable)

3. PATIENT SELECTION, ENROLMENT, RANDOMISATION, RESTRICTIONS, DISCONTINUATION AND WITHDRAWAL

This study can fulfill its objectives only if appropriate subjects are enrolled. The following eligibility criteria are designed to select subjects for whom participation in the study is considered appropriate. All relevant medical and nonmedical conditions should be taken into consideration when deciding whether a particular subject is suitable for this protocol.

Subject eligibility should be reviewed and documented by the investigator or appropriate member his/her site study team before subjects are included in the study. Each patient should meet all of the inclusion criteria and none of the exclusion criteria for this study. Under no circumstances can there be exceptions to this rule.

3.1. Inclusion criteria

For inclusion in the study patients should fulfil the following criteria:

1. Informed consent in writing from parent(s) or other legally-acceptable representative(s)
2. Male or female, gestational age ≥ 34 weeks, and chronological age 7 to <60 days at the time of screening

3. Diagnosis of sepsis within 36 hours before enrolment, defined as the presence of at least 2 clinical criteria and at least 1 laboratory criterion in the presence of or as a result of suspected or proven bacterial infection that requires IV antibiotic therapy.
4. Patients must meet at least 2 of the following clinical criteria:
 - a. Hypothermia ($<36^{\circ}\text{C}$) OR fever ($>38.5^{\circ}\text{C}$)
 - b. Bradycardia OR tachycardia OR rhythm instability
 - c. Urine output 0.5 to 1 mL/kg/h OR hypotension OR mottled skin OR impaired peripheral perfusion
 - d. Petechial rash OR sclerema neonatorum
 - e. New onset or worsening of apnoea episodes OR tachypnoea episodes OR increased oxygen requirements OR requirement for ventilation support
 - f. Feeding intolerance OR poor sucking OR abdominal distension
 - g. Irritability
 - h. Lethargy
 - i. Hypotonia.
5. Patients must meet at least 1 of the following laboratory criteria:
 - a. White blood cell count $\leq 4.0 \times 10^9/\text{L}$ OR $\geq 20.0 \times 10^9/\text{L}$
 - b. Immature to total neutrophil ratio >0.2
 - c. Platelet count $\leq 100 \times 10^9/\text{L}$
 - d. C-reactive protein (CRP) $>15 \text{ mg/L}$ OR procalcitonin $\geq 2 \text{ ng/mL}$
 - e. Hyperglycaemia OR Hypoglycaemia
 - f. Metabolic acidosis.

3.2. Exclusion criteria

Patients should not enter the study if any of the following exclusion criteria are fulfilled:

1. Documented history of any hypersensitivity or allergic reaction to any β -lactam antibiotic or aminoglycoside

2. At study entry, has confirmed infection with a pathogen known to be resistant to the combination of ceftaroline fosamil, ampicillin, and the optional aminoglycoside of choice OR confirmed viral, fungal, or parasitic pathogen as the sole cause of infection
3. Refractory septic shock within 24 hours before enrolment that does not resolve after 60 minutes of vasopressor therapy
4. Moderate or severe renal impairment defined as serum creatinine ≥ 2 times the upper limit of normal (\times ULN) for age OR urine output < 0.5 mL/kg/h (measured over at least 8 hours) OR requirement for dialysis
5. Evidence of progressively fatal underlying disease, or life expectancy of ≤ 60 days
6. Documented history of seizure
7. Requiring or currently taking antiretroviral therapy for human immunodeficiency virus (HIV) or a child from an HIV positive mother
8. Proven or suspected central nervous system (CNS) infection (eg, meningitis, brain abscess, subdural abscess), osteomyelitis, endocarditis, or necrotizing enterocolitis (NEC)
9. Any condition (eg, cystic fibrosis, urea cycle disorders), antepartum/peripartum factors, or procedures that would, in the opinion of the investigator, make the patient unsuitable for the study, place a patient at risk, or compromise the quality of data
10. Patient's parent(s) or legally-acceptable representative(s) involvement in the planning and/or conduct of the study (applies to both Sponsor staff and/or staff at the study site). Concurrent participation in another clinical study with an investigational product (IP), previous enrolment/participation in this study, or participation in another study of ceftaroline fosamil within 14 days before the intended start of the first dose of study therapy.

For procedures for withdrawal of incorrectly enrolled patients see [Section 3.4](#).

3.3. Patient enrolment

This is a non-randomized open-label study. Patients will be enrolled if they meet all the inclusion criteria, including informed consent in writing from parent(s) or other legally-acceptable representative(s), and none of the exclusion criteria. Patients will be stratified by age cohort as described in [Section 3.5.1](#). Patients will be randomly assigned in the PK portion of the study to PK Schedule 1 or 2 ([Section 3.5.2](#)).

The investigator(s) will be responsible for patient management. Assessments and procedures should be conducted as noted in [Section 4](#). The Pharmacist or designee will prepare study therapy infusions and manage dose adjustments, as applicable.

Patients who are withdrawn from study before receiving any amount of study therapy will be replaced in order to enrol a total of 24 treated patients for safety evaluations.

3.4. Procedures for handling incorrectly enrolled patients

Patients who fail to meet the eligibility criteria should not, under any circumstances, receive study medication. There can be no exceptions to this rule. Patients who are enrolled, but subsequently found not to meet all the eligibility criteria must not be initiated on treatment.

Where a patient does not meet all the eligibility criteria but is incorrectly started on treatment, the investigator should inform the Sponsor study physician/designee immediately, and a discussion should occur between the Sponsor study physician/designee and the investigator regarding whether to continue or discontinue the patient from treatment. The Sponsor study physician/designee must ensure all decisions are appropriately documented.

3.5. Methods for assigning treatment groups

3.5.1. Stratification by age and cohort

This study is not randomized, but patients will be stratified by age cohort and randomly assigned for assessment of PK to PK Schedule 1 or 2 ([Section 3.5.2](#)).

At least 24 patients evaluable for safety will be enrolled and treated within the following age cohorts:

- Cohort 1: young infants aged >28 days to <60 days (n=8)
- Cohort 2: term neonates (defined as gestational age \geq 37 weeks) aged 7 to \leq 28 days (n=8)
- Cohort 3: preterm neonates (defined as gestational age \geq 34 to <37 weeks) aged 7 to \leq 28 days (n=8).

3.5.2. Assignment to PK schedule

Two PK samples (approximately 0.3 to 0.6 mL per draw) will be obtained at steady state from at least 20 patients. Patients will be randomly assigned (1:1) at the time of enrolment to one of the PK sample collection schedules:

- PK Schedule 1: at the end of the ceftaroline fosamil infusion (\pm 5 minutes) and 3 to 4 hours after the end of the infusion
- PK Schedule 2: 15 minutes to 2 hours after the end of the ceftaroline fosamil infusion and 5 to 7 hours after the end of the infusion (before the start of the next infusion)

3.6. Methods for ensuring blinding

This study is not blinded. The investigators, pharmacists or designees, study centre personnel, and parent(s)/legally-acceptable representative(s) will be aware of study therapy being administered.

3.7. Methods for unblinding

The study is not blinded.

3.8. Restrictions

Concomitant use of potentially effective systemic antibacterial therapy (other than study therapy), or any drug known to exhibit a contraindicated drug-drug interaction with any study therapy or labelled contraindication to use of any study therapy is not allowed.

3.9. Discontinuation of investigational product

At any time, parent(s) or legally-acceptable representative(s) are free to discontinue the patient from treatment with IP or withdraw the patient from the study (ie, IP and assessments – see [Section 3.10.2](#)), without prejudice to further treatment. Parent(s) or legally-acceptable representative(s) who decide to discontinue a patient from treatment with IP will always be asked about the reason(s) and the presence of any adverse events. If possible, the patient will be seen and assessed by an investigator(s). Adverse events will be followed up until SFU, 28 to 35 days after the last dose of study therapy (See [Section 6](#)). Any AEs that are unresolved at the patient's last AE assessment in the study are followed up by the investigator for as long as medically indicated, but without further recording in the CRF.

3.9.1. Procedures for discontinuation of a patient from investigational product

3.9.1.1. Discontinuations Due to Safety

Assessments and Procedures: A patient who is prematurely discontinued from study therapy administration for safety reasons should have EOT assessments conducted per [Section 4.2.5](#) and undergo subsequent assessments at TOC and SFU.

Clinical Outcome Assessment: If a patient is prematurely discontinued from study therapy due to an AE and the clinical signs and symptoms of sepsis have resolved completely or improved such that no further antibacterial therapy is necessary, the patient should be assessed as a clinical cure at EOT and reassessed at TOC.

If a patient is prematurely discontinued from study therapy due to a study therapy-related AE and requires alternative non-study antibacterial for treatment for LOS, the patient should be assessed as a clinical failure.

Reasons for premature discontinuation from study therapy administration due to safety may include, but are not limited to, occurrence of an AE that, in the opinion of the investigator, warrants the patient's permanent discontinuation from study therapy administration.

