8.4. Outcome measures for analyses

8.4.1. Efficacy response definitions

8.4.1.1. Clinical outcome at End-of-Therapy

An assessment of clinical outcome will be made by the investigator at EOT. The clinical outcome categories are defined in [Table 4](#). A favourable clinical outcome is clinical cure. An outcome of clinical failure at EOT will be carried forward to TOC.

Table 4 Clinical outcome categories at End-of-Therapy

Outcome	Definition
Clinical Cure	Resolution of all acute signs and symptoms of LOS or improvement to such an extent that no further antibacterial therapy is required
Clinical Failure	Patients who received ≥ 48 hours of study treatment and meet any of the following: 
• Discontinuation of study therapy due to insufficient therapeutic effect, including persistence, incomplete clinical resolution, worsening in signs and symptoms of LOS, or isolation of a resistant pathogen that requires alternative nonstudy antibacterial therapy• Discontinuation of study therapy due to a study therapy-related AE and requirement for alternative nonstudy antibacterial therapy for LOS• Death in which LOS is contributory
Indeterminate	Study data are not available for evaluation of efficacy for any reason, including: 
• Death in which LOS is clearly noncontributory• Lost to follow-up• Extenuating circumstances precluding classification as a cure or failure• Diagnosis of CNS infection, osteomyelitis, endocarditis, or NEC at any time after enrolment• Received < 48 hours of study therapy

Abbreviations: AE=adverse event; CNS=central nervous system; LOS=late-onset sepsis; NEC=necrotizing enterocolitis.

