8.4.1.2. Clinical outcome at Test-of-Cure

An assessment of clinical outcome will be made by the investigator at TOC. The clinical outcome categories are defined in [Table 5](#). A favourable clinical outcome is clinical cure.

Table 5 Clinical outcome categories at Test-of-Cure

Outcome	Definition
Clinical Cure	Resolution of all acute signs and symptoms of LOS or improvement to such an extent that no further antibacterial therapy is required
Clinical Failure	Patients who received ≥ 48 hours of study treatment and meet either of the following criteria: 
• Incomplete resolution or worsening of LOS signs or symptoms or development of new signs or symptoms, or isolation of a resistant pathogen requiring alternative nonstudy antibacterial therapy• Death in which LOS is contributory
Indeterminate	Study data are not available for evaluation of efficacy for any reason, including: 
• Death in which LOS is clearly noncontributory• Lost to follow-up• Extenuating circumstances precluding classification as a cure or failure• Diagnosis of CNS infection, osteomyelitis, endocarditis, or NEC at any time after enrolment• Received <48 hours of study therapy

Abbreviations: CNS=central nervous system; LOS=late-onset sepsis; NEC=necrotizing enterocolitis.

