The study design is described in the Study Diagram ([Figure 1](#)). Patient participation will require up to 49 days (up to 14 days of treatment plus up to 35 days of safety follow-up). The total duration of study therapy is 48 hours (minimum) to 14 days (maximum). Hospitalization is required during IV study therapy. Baseline assessments for study eligibility will occur within 36 hours before the first dose of study therapy.

Procedures will be performed according to the Study Plan in [Table 1](#). Safety assessments will be done throughout the study. Between Day 2 and Day 14, 2 blood samples will be collected for PK analysis. The efficacy of ceftaroline fosamil will be evaluated based on the clinical outcome (clinical cure, clinical failure or indeterminate) at end of therapy (EOT; within 24 hours after completion of last infusion) and test-of-cure (TOC; 8 to 15 days after the last dose of study therapy) assessments. The Safety Follow-up (SFU) assessments will occur 28 to 35 days after the last dose of study therapy. Adverse events (AEs) will be followed up in the study until SFU.

A patient who is prematurely discontinued from study therapy administration for any reason will have EOT assessments conducted and undergo subsequent safety assessments at TOC and SFU per protocol.

[figure not shown]
- If a patient is prematurely discontinued from study therapy due to an adverse event and the clinical signs and symptoms of sepsis have resolved completely or improved such that no further antibacterial therapy is necessary, the patient will be assessed as a clinical cure at EOT and reassessed at TOC.
- If a patient is prematurely discontinued from study therapy due to a study therapy-related AE and requires alternative non-study antibacterial for treatment for LOS, the patient will be assessed as a clinical failure (or indeterminate, if the patient discontinued before minimum treatment duration) at EOT and TOC.
- If a patient is prematurely discontinued from study therapy administration (at any time after the required minimum treatment duration of 48 hours) due to insufficient therapeutic effect, the patient will be assessed as a clinical failure on the day of discontinuation (ie, EOT) and at all subsequent evaluation time points.

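### An infant stopped before 48 hours for an adverse event can be rated cure, failure or indeterminate depending on which section is followed, and the plan gives no precedence

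*Protocol*

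**What the plan says.** Two sentences in Protocol 3.9.1.1 tell the investigator how to rate an infant whose study therapy is stopped early for an adverse event (AE).

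- If the signs of sepsis have resolved, or the infant has "improved such that no further antibacterial therapy is necessary, the patient should be assessed as a clinical cure at EOT and reassessed at TOC".
- Where the AE is related to study therapy and the infant "requires alternative non-study antibacterial for treatment for LOS, the patient should be assessed as a clinical failure".

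Neither sentence mentions how long the infant was treated.

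SAP 1.2 repeats both rules but treats them differently. On the cure side, "the patient will be assessed as a clinical cure at EOT and reassessed at TOC", with no duration limit. On the failure side, the rating is "clinical failure (or indeterminate, if the patient discontinued before minimum treatment duration) at EOT and TOC". The same section gives the minimum: "The total duration of study therapy is 48 hours (minimum) to 14 days (maximum").

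The outcome definitions are in Protocol 8.4.1.1 and 8.4.1.2 and SAP 3.2.1.1 (Tables 4 and 5 in each document). The indeterminate row includes "Received < 48 hours of study therapy" at end of therapy (EOT) and "Received <48 hours of study therapy" at test of cure (TOC), with no exception for infants who are well. The failure row requires at least 48 hours of treatment. The cure row has no duration condition.

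**The concern.** An infant who stops at, say, 24 hours for an AE and needs no more antibiotic fits both the cure row and the indeterminate row of the same table. The text in Protocol 3.9.1.1 and SAP 1.2 points to cure. Nothing says which prevails.

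The mirror case, an early stop for a related AE with a switch to another antibacterial, is a failure under Protocol 3.9.1.1 and indeterminate under SAP 1.2 and the tables. Within the SAP, therefore, the 48-hour limit binds failure but not cure.

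At stake is the cure rate in the modified intent-to-treat (MITT) set. That set admits any infant given any amount of ceftaroline fosamil, so early stops are in it. Two programmers who both follow the plan could report different cure, failure and sensitivity results from the same data.

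**Working it through.** **1. The rules side by side, for an AE stop before 48 hours**

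| Source | Well, no further antibacterial | Related AE, other antibacterial needed |
|---|---|---|
| Protocol 3.9.1.1 | Cure at EOT, reassessed at TOC | Failure |
| SAP 1.2 | Cure at EOT, reassessed at TOC | Indeterminate at EOT and TOC |
| Tables 4 and 5, both documents | Fits the cure row and the indeterminate row | Indeterminate |

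**2. Does the derivation settle it?** SAP Table 6 combines the investigator's EOT and TOC ratings and checks no duration.

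- EOT cure + TOC cure gives cure.
- EOT cure + TOC indeterminate gives indeterminate.
- EOT indeterminate + TOC cure gives cure.

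So the TOC result depends on whether the investigator applies the 48-hour row of Table 5 at reassessment. Even an infant coded indeterminate at EOT re-enters the numerator if rated cure at TOC.

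**3. Would the exposure variable catch it?** SAP 3.3.3 counts calendar days: last date minus first date plus 1. With dosing every 8 hours, a first infusion at 23:00 on one date and a last at 07:00 two dates later are 1 + 24 + 7 = 32 hours apart, yet count as 3 days. The variable cannot identify stops before 48 hours. Infusion date and time, which can, are recorded under Protocol 7.5.

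**4. Size.** The plan states no expected cure rate, so there is no figure to reproduce beyond 3 × 8 = 24. Inputs: n = 24 overall and 8 per cohort (SAP 1.3), taking all planned infants to be in the MITT set. Cure rate = cures / (cures + failures + indeterminates) (SAP 3.2.1.1). The 95% Jeffreys interval (SAP 4.2.7.1) is the 2.5th and 97.5th percentiles of Beta(x + 0.5, n − x + 0.5).

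One infant moves the rate by 1/24 = 4.2 points overall and 1/8 = 12.5 points in a cohort. With an assumed 18 other cures overall, or 6 in a cohort:

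| Early stops counted as cure | Overall | Cohort of 8 |
|---|---|---|
| 0 | 18/24 = 75.0% (55.5 to 88.8) | 6/8 = 75.0% (40.8 to 94.4) |
| 1 | 19/24 = 79.2% (60.2 to 91.6) | 7/8 = 87.5% (54.6 to 98.6) |
| 2 | 20/24 = 83.3% (65.1 to 94.1) | not shown |

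**5. Cure and failure sides together.** Assume 20 infants treated for at least 48 hours (16 cures, 4 failures) and 4 early stops for a related AE (2 well, 2 needing another antibacterial). The sensitivity analysis drops indeterminates.

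| Rule followed | Cure | Failure | Sensitivity cure rate |
|---|---|---|---|
| 48-hour row of the tables, strictly | 16/24 = 66.7% | 4/24 = 16.7% | 16/20 = 80.0% |
| SAP 1.2 text | 18/24 = 75.0% | 4/24 = 16.7% | 18/22 = 81.8% |
| Protocol 3.9.1.1 text | 18/24 = 75.0% | 6/24 = 25.0% | 18/24 = 75.0% |

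The last two rows have the same main cure rate: recoding an early non-cure from indeterminate to failure leaves both numerator and denominator unchanged. It moves only the failure rate and the sensitivity analysis.

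**The case against.** The best defence is that Tables 4 and 5 are the definitions. Protocol 5.1 and SAP 3.2.1.1 point to them, they name under 48 hours as indeterminate without exception, and SAP 1.2 is a design summary. That is the more natural reading, but it is not secured. The cure row in those tables has no duration condition, Protocol 3.9.1.1 is a direct instruction to the person whose rating is analysed, and SAP 1.2 itself writes the limit into one bullet and not the other.

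Several stronger readings are tempting, and the documents do not support them.

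- A reader might infer that early stops can add cures but never failures. That is true of SAP 1.2 and the tables, not of Protocol 3.9.1.1, whose failure sentence is equally unlimited.
- A reader might infer that the lost failures inflate the main cure rate. They do not, because indeterminates stay in the denominator.
- A reader might take the TOC rate to be inflated in every case. If Table 5 is applied at TOC, Table 6 returns indeterminate.
- A reader might suppose that every such infant with a baseline pathogen gains a favourable microbiological response. Presumed eradication applies only where no source specimen was available to culture.
- That these infants are the least likely to have had bacterial sepsis has no source in the documents.

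It also stands that numbers should be small. Protocol 1.3 gives 35/1300 = 2.7% stopping for AEs in pooled Phase III trials. Applied to 24 infants this is 24 × 35/1300 = 0.65 at any time, and early stops who are well are a subset. That rate may not carry over to neonates. Patient-level listings of outcome and ceftaroline administration are already planned, so a careful reader could find the cases.

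**Conclusion.** The contradiction is in the text and holds on both sides: cure against indeterminate for the early stop who is well, and failure against indeterminate for the early stop who needs another antibacterial.

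The effect on the EOT cure rate is direct, at 4.2 points overall or 12.5 points in a cohort for each infant. The effect on the TOC rate is conditional on the investigator's cure rating standing against Table 5. The failure rate and the sensitivity analysis also depend on the rule chosen.

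The sizes assume planned numbers, all in the MITT set. The count of affected infants, 0 to 2, is an assumption that the documents do not inform, and at 0 nothing changes. Efficacy is a secondary objective with no hypothesis test, so this is a question of reproducible reporting and not of error control. It is worth correcting because the remedy is cheap and a cohort holds only 8 infants.

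**What to change.** Reconcile the passages under one precedence rule for stops before 48 hours, the same for cure and failure, in:

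- both sentences of Protocol 3.9.1.1 (amending the cure sentence alone would create the opposite asymmetry);
- both AE bullets of SAP 1.2;
- the Clinical Cure rows of Tables 4 and 5 in both documents;
- the SAP Table 6 derivation.

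The choice consistent with the tables' explicit row is to analyse under 48 hours as indeterminate at both EOT and TOC. Derive this in the SAP from the recorded infusion dates and times, stating which infusions start and end the 48 hours, and apply it before Table 6 so that a TOC cure cannot override it. Keep the investigator's rating in the listing and flag these infants.

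The cost is wording in two documents and one programmed check on data already collected. The cure rate may become slightly less favourable.
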